A study carried out by Bendstrup, et al (2002),¹⁷ evaluated the effects of the inhibition of systemic coagulation through nebulized unfractionated heparin at doses up to 64 mg and identified that there is a dose-dependent effect for factor Xa inactivation, inducing minimal changes in aPTT, and it is safe for clinical or research purposes, without increasing the risk of bleeding.¹⁸

Phelps, et al (2020),¹⁹ carried out a systematic review on the use of UFH inhalation for the treatment of inhalation injury caused by heat in burn patients and concluded that nebulized heparin did not demonstrate an increase in the risk of bleeding rates and decreased the duration of mechanical ventilation.

For COVID-19, the heparin anti-viral effect is expected to be related to the fact that heparin blocks viral interaction with host receptors thereby inhibiting virus interaction with the cell and, consequently, viral invasion.^{20, 21} To this moment, some studies indicate that treatment with systemic heparin reduced hospital mortality in patients with COVID-19²² and a previous study that strongly supported the clinical investigation of heparin as a potential treatment for patients with COVID-19,^{23, 24} justifies further investigation to prove these clinical effects.

Objectives

Primary objectives assessment

Safety: related to the use of nebulized enriched heparin by patients with SARS-CoV-2 through the assessment of hemorrhagic events of any nature, alteration of the coagulation testing, like prolonged activated partial thromboplastin time (aPTT), indicated by an increase in aPTT>1.5, and heparin-induced thrombocytopenia; Efficacy: related to the proposed treatment, through analysis of the SARS-CoV-2 viral load of the participants treated by the sequential assessment of reverse transcription-polymerase chain reaction (RT-PCR) in the nasal swab.

Secondary objectives assessment

Safety measured by respiratory, clinical, laboratorial and tomographic findings as follows, in number of patients, and hospitalization days:

Supplemental oxygen therapy needed;

Mechanical pulmonary ventilation needed;

Renal failure development;

Development of major cardiovascular events such as pulmonary embolism and acute myocardial infarction;

Demand for intensive care unit (ICU) treatment;

Secondary pulmonary bacterial infections (bacterial pneumonia);

Deep vein thrombosis (DVT) through Doppler ultrasonography assessment;

Pancreatitis characterized by increase in amylase >200 U/L;

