Demand for corticosteroid therapy such as hydrocortisone, dexamethasone and other corticosteroids due to inflammatory pulmonary disease;

Death;

Increase in white blood cell count (>10.000 cells/mm³);

Increase in C reactive protein test (CRP) (>3.00mg/L);

Deterioration of arterial blood gas paO₂/pFiO₂ ratio (<200);

Altered sodium (< 135mEq/L or > 145mEq/L);

Altered potassium (< 3,5mEq/L or > 5,5mEq/L);

Worsening of pulmonary area compromised (%) by inflammation or infection through tomographic assessment.

Method

EnHanCed study design

The present protocol refers to a phase I / II, prospective, randomized, parallel, triple blind clinical trial. This design is justified by the lack of a drug-specific cost-efficient treatment for SARS-CoV-2 patients. The use of a therapeutic drug justifies the need for a placebo control group. A minimum number of participants will be allocated to this study, as the main intention will be to evaluate the safety of the treatment. Triple blind clinical studies have the lowest levels of bias and, therefore, the highest level of evidence for a clinical study. It is understood that there is no need for a purely phase I study based on the literature data previously presented.

The study will be carried out at the São Paulo State University (UNESP) Clinical Hospital of the Botucatu Medical School, Botucatu, São Paulo, Brazil.

Dosage and administration

Considering the pulmonary water loss of 8 to 10mL during the gas exchange in 30 minutes (of inhalation) and compensating the dilution of the solution in the pulmonary fluids, we opted for the dose of 2.5 mg heparin in 10mL of 0.9% saline solution, aiming the effective mean tested doses (62.5 μ g/mL to 250 μ g/mL), nebulized 4/4 hours, except the nebulization that would be administered between 12 pm and 6 am. The treatment will be administered for 7 days because it will be assumed that the reduction in viral load promoted by enriched heparin will have a significant impact during the first 14 days of the infectious process. Considering that the patient has already had the disease for at least seven days when admitted and that the viral load tends to reduce spontaneously after the referred period, it is known that complications persist due to other factors such as inflammatory response.

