The total recruitment size will be 50 participants, aiming at 40 patients followed during the study period. The sample was estimated considering the number of patients diagnosed as COVID-19 at the São Paulo State University (UNESP) Clinical Hospital that met the study's eligibility criteria.

The sample calculation of 40 patients took into account two independent study arms, with an estimated proportion in the viral load reduction rate of 30% for group 1, that will receive placebo, and 75% for group 2 that will be treated with enriched nebulized heparin as proposed in this study, considering 80% test power and a 5% significance level for a bilateral test.

Categorical variables will be evaluated with Fisher's exact test, continuous variables will be compared with non-parametric methods such as Mann-Whitney test or U test, paired comparisons will be evaluated with the Wilcoxon test, multivariate analyzes will be evaluated with regression Cox analysis and long-term clinical analyzes will be compiled on Kaplan-Meir curves.

Interventions and inpatient schedule

Intervention	Day 0	Day 1	Day 2	Day 3	Day 4	Day 5	Day 6	Day 7	Day 8
Informed consent form	X								
Medical visit, patient story and physical examination	X	X	X	X	X	X	X	X	X
Vital signs assessment	X	X	X	X	X	X	X	X	X
Medications in use	X	X	X	X	X	X	X	X	X
Inclusion and exclusion criteria	X								
COVID-19 viral load in RT-qPCR	X		X			X		X	X
Complete blood count, D-dimer, aPTT, urea, creatinine, glucose, reactive protein C, blood gas and amylase	X		X			X		X	X
Computed thoracic tomography	X								X
HMWH or placebo administration		X	X	X	X	X	X	X	X
Adverse events	X	X	X	X	X	X	X	X	X
Discontinuation criteria	X	X	X	X	X	X	X	X	

Table 1. Schedule for assessments and intervention. The participants will be followed up and evaluated on days 0, 1, 2, 3, 4, 5, 6, 7 and 8 days after randomization.

The closure assessment will be carried out on day 8. Extra data can be collected if the patient's clinical condition changes. Randomization will be performed in up to 24 hours after admission. After the end of the study, the participant will be referred and accompanied at the COVID-19 outpatient clinic São Paulo State University (UNESP) Clinical Hospital.

Adverse events

Adverse effects related to the nebulized use of heparins will be tracked and analyzed according to the Common Terminology Criteria for Adverse Events (CTC-AE 5.0),²⁵ and will be graded from 1 to 5, accordingly to the severity of the event.

Grade	Description

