Aphasia	Yes 	No 	
Aphasia start date (blank if not present)			
Aphasia end date (blank if still present)			
Hyporexia	Yes 	No 	
Hyporexia start date (blank if not present)			
Hyporexia end date (blank if still present)			
Heart rate (BPM)			

Brachial systolic pressure (mmHg)					
Brachial diastolic pressure (mmHg)					
Peripheral oxygen saturation (%)					
Axillary temperature (Celsius)					
Paleness	Normal 	1+/4+ 	2+/4+ 	3+/4+ 	4+/4+ 
Cyanosis	Normal 	1+/4+ 	2+/4+ 	3+/4+ 	4+/4+ 
Oral cavity	Normal 	Altered 			
Description					
Pulmonary auscultation	Normal 	Altered 			
Description					
Cardiac auscultation	Normal 	Altered 			
Description					
Abdominal examination	Normal 	Altered 			
Description					
Limbs (pulses, edema, skin conditions)	Normal 	Altered 			
Description					

Figure 2. Clinical assessment and physical examination form based on SARS-CoV-2 most prevalent symptoms.

Laboratory results and tomographic findings form			
Form Number:	Date:		
RT-qPCR	Positive 	Negative 	
RT-qPCR quantitative viral load			
Blood count	Normal 	Altered 	
Hemoglobin (g / dL)			
Hematocrit (%)			
Mean corpuscular volume (fL)			
Red cell distribution width (%)			
Platelets count (10³ / µL)			
White cell count (10³ / µL)			
Neutrophils (%)			
Lymphocytes (%)			
Bands (%)			
Arterial gas	Normal 	Altered 	
pH			
pCO₂ (mmHg)			
PaO₂ / FiO₂			
HCO₃ (mEq / L)			
SO₂ (%)			
Base Excess			
D-Dimer (µg / mL)			
aPTT	Normal 	Altered 	
Prothrombin time (PT)			
International normalized ratio (INR)			
Activated partial thromboplastin time (aPTT)			
Normalized aPTT Ratio			
Renal function	Normal 	Altered 	
Urea (mg / dL)			
Creatinine (mg / dL)			

Fasted glucose (mg / dL)	
C reactive protein (CRP) (mg / L)	
Amylase (U / L)	
Thoracic tomography description	

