Figure 3. Laboratory and tomographic findings form based on SARS-CoV-2 inpatient laboratorial routine.

Adverse events form					
Form Number:	Date:				
Thrombotic thrombocytopenic purpura	Grade 1 	Grade 2 	Grade 3 	Grade 4 	Grade 5 
Time between event and last dose administered (hours)					
Disseminated intravascular coagulation	Grade 1 	Grade 2 	Grade 3 	Grade 4 	Grade 5 
Time between event and last dose administered (hours)					
Hemorrhage	Grade 1 	Grade 2 	Grade 3 	Grade 4 	Grade 5 
Site of hemorrhage					
Time between event and last dose administered (hours)					
Anaphylaxis	Grade 1 	Grade 2 	Grade 3 	Grade 4 	Grade 5 
Time between event and last dose administered (hours)					
Hypophysitis	Grade 1 	Grade 2 	Grade 3 	Grade 4 	Grade 5 
Time between event and last dose administered (hours)					
Ischemia	Grade 1 	Grade 2 	Grade 3 	Grade 4 	Grade 5 
Site of Ischemia					
Time between event and last dose administered (hours)					
Other adverse events (description)					
Grading	Grade 1 	Grade 2 	Grade 3 	Grade 4 	Grade 5 
Time between event and last dose administered (hours)					
Other adverse events (description)					
Grading	Grade 1 	Grade 2 	Grade 3 	Grade 4 	Grade 5 
Time between event and last dose administered (hours)					
Other adverse events (description)					
Grading	Grade 1 	Grade 2 	Grade 3 	Grade 4 	Grade 5 
Time between event and last dose administered (hours)					

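### Altered sodium and altered potassium are secondary safety outcomes, but neither appears in the laboratory schedule or on the laboratory form; the oxygen outcome also needs a Day 0 reference

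*Combined protocol and SAP*

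**What the plan says.** **Outcomes.** The section on secondary objectives lists safety outcomes to be reported "in number of patients, and hospitalization days". Two of them are electrolyte outcomes with numeric limits: "Altered sodium (< 135mEq/L or > 145mEq/L") and "Altered potassium (< 3,5mEq/L or > 5,5mEq/L"). The same list opens with "Supplemental oxygen therapy needed", with no further definition.

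**Schedule.** The laboratory row of Table 1, marked for Days 0, 2, 5, 7 and 8, reads "Complete blood count, D-dimer, aPTT, urea, creatinine, glucose, reactive protein C, blood gas and amylase".

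**Laboratory form.** The "Laboratory results and tomographic findings form" has an arterial gas block (pH, pCO2, PaO2/FiO2, HCO3, SO2, base excess) and a renal block (urea, creatinine). It also has fields for blood count, coagulation, D-dimer, glucose, CRP and amylase. Its caption describes it as "Laboratory and tomographic findings form based on SARS-CoV-2 inpatient laboratorial routine".

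**Unscheduled data.** Below Table 1 the protocol adds that "Extra data can be collected", on condition that the patient's clinical state changes.

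**Oxygen.** The eligibility criteria admit patients whose oxygen demand is under 5 L/min. The clinical assessment form is dated and records supplementary oxygen as yes or no, without flow. Table 1 plans a medical visit on every day from 0 to 8. The nebulizer may be driven by oxygen or by compressed air.

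**The concern.** An outcome with a cut-off needs a planned measurement and somewhere to record it. Sodium and potassium have neither. If staff follow Table 1 and fill in the form as printed, the report cannot say how many patients in each arm crossed the limits. Nor can it separate values already abnormal at entry from those that became abnormal on treatment. The protocol gives safety as the trial's main purpose, so a listed safety outcome should not lack data by design.

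The oxygen item has a milder form of the same problem. Data are collected, but no rule says how a patient already on oxygen at Day 0 is counted. Read literally, that patient is an event before the first nebulization.

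**Working it through.** No figure in the plan bears on this point, so the check sets the outcome list against the schedule and the form.

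**1. Secondary outcomes with a laboratory cut-off**

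| Outcome | Limit | Table 1 laboratory row | Laboratory form field |
|---|---|---|---|
| Amylase (pancreatitis) | >200 U/L | yes | yes |
| White cells | >10,000 cells/mm³ | yes (blood count) | yes |
| CRP | >3.00 mg/L | yes | yes |
| PaO2/FiO2 | <200 | yes (blood gas) | yes |
| Sodium | <135 or >145 mEq/L | **no** | **no** |
| Potassium | <3.5 or >5.5 mEq/L | **no** | **no** |

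Four of six are in both places and two of six are in neither. The adverse events form has no electrolyte item either, only free-text lines for other events. This pattern looks like an oversight, not a convention of leaving routine tests unlisted.

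**2. What the loss amounts to.** The outcomes count patients, so what is missing is two yes/no results per patient: 2 × 40 = 80 for the 40 patients to be followed, or 2 × 50 = 100 for all 50 recruited.

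**3. Oxygen: what the yes/no field can and cannot show.** This assumes that the clinical form is completed at each daily visit.

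| Status at Day 0 | Later course | Literal count | Available from the daily yes/no field |
|---|---|---|---|
| No oxygen | none | not an event | yes |
| No oxygen | starts oxygen | event | yes, as new need |
| On oxygen | unchanged or weaned | event | yes, as need at entry; days on oxygen can be counted |
| On oxygen | flow increased | event | no, cannot be told apart from unchanged need |

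Only the last row needs data that are not collected. PaO2/FiO2 and the non-invasive and mechanical ventilation fields capture part of it.

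**4. Direction of the effect.** Let s be the share on oxygen at entry, and c and t the rates of new need in the control and treated arms among patients not on oxygen at entry.

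- Literal count: s + (1 − s)c against s + (1 − s)t.
- New need only, over all patients: (1 − s)c against (1 − s)t.
- In both, the difference is (1 − s)(c − t).

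The literal count adds s to each arm, a part that treatment cannot change. It also carries any chance imbalance in s straight into the comparison. Counting new need removes that part but still leaves out patients who enter on oxygen. Only a flow record brings them in. The documents do not give s. The entry wording can be read to admit patients on no oxygen or to require some demand. Under the second reading s = 1, and the literal count is every patient in both arms.

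**The case against.** **A blood gas analyser or routine care may supply sodium and potassium.** This is possible. The caption says only that the form is based on the hospital's routine, which does not make it exhaustive. Table 1 is not a full list of what is measured: the form has fields for prothrombin time and INR, which the Table 1 row does not name. So a reader might infer that the two electrolytes will never be measured, and the documents do not support that. What stands is narrower. Prothrombin time and INR at least have a field, whereas sodium and potassium have neither a schedule entry nor a field, and nothing in the text says where their values would come from. The provision for extra data depends on clinical change. It would yield values from selected patients, with no systematic baseline.

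**The oxygen outcome can be rescued in the analysis.** This is largely right. The dated daily field gives Day 0 status, new need and days on oxygen, and the last of these fits the reference to days in the outcome heading. The counting rule can still be set before unblinding. Only flow is not captured. PaO2/FiO2 on five days, the ventilation fields, and the intensive care and death outcomes cover part of any worsening.

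**A large loss of power.** A reader might infer that the oxygen wording costs a definite amount of power. The documents give neither the share on oxygen at entry nor an expected effect, and the answer swings with both. With 20 per arm and a two-sided Fisher test at 5%, power for new or increased need is about 74% if the rates are assumed to be 50% against 10%. It is about 24% at 30% against 10%. Both pairs are invented for illustration, and the trial was sized on viral load, so no power figure can be claimed.

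**Conclusion.** The electrolyte mismatch holds and can be checked directly against the text. Two of the six secondary outcomes with a laboratory cut-off have no planned measurement and no place on the form, so they cannot be assessed systematically as the protocol stands. It should be corrected, but it does not touch the primary outcomes or the sample size.

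A reader might multiply out 2 analytes × 5 draws × 40 patients = 400 lost values (500 for 50 patients). That overstates the loss. The outcomes count patients, and the withdrawal and discontinuation rules mean that not everyone would complete all five draws.

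The oxygen point holds as a secondary matter of definition. The literal count mixes need before treatment with need after it, by an amount that depends on an unstated entry share. Most of this can be resolved with data already collected. A reader might infer that the oxygen outcome is unusable, but the daily field does not bear that out.

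The conclusion assumes that the clinical form is completed daily. It also assumes that the text between the adverse events form and the start of the reference list, which was not available in the copy read, adds no laboratory tests. Its position makes that likely, but it could not be checked.

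**What to change.** 1. Add sodium and potassium to the Table 1 laboratory row, on the existing draws at Days 0, 2, 5, 7 and 8, and add two fields to the laboratory form. Alternatively, delete both outcomes.
2. Define the oxygen outcome relative to Day 0 status, using the daily yes/no field. State that gas used only to drive the nebulizer does not count as supplemental oxygen.
3. Preferably add a daily flow field (L/min) to the clinical form, so that increased need can be counted in patients already on oxygen at entry.

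**Cost.** Two more analytes on draws already planned, a few form fields, one defining sentence, and no extra visits. Counting relative to Day 0 gives fewer oxygen events. Deleting the electrolyte outcomes costs nothing to run but gives up that safety information. The oxygen counting rule can be written at any time before unblinding. Electrolyte values and flow need to be recorded prospectively, since the documents name no other source from which to recover them.

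### Altered sodium and altered potassium each pool low and high values in one count, so a one-directional effect could be diluted, cancelled or shown as fewer events

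*Combined protocol and SAP*

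**What the plan says.** Under 'Secondary objectives assessment' the protocol lists "Altered sodium (< 135mEq/L or > 145mEq/L" and "Altered potassium (< 3,5mEq/L or > 5,5mEq/L", each as a single outcome. The opening line of that list says the findings are measured "in number of patients, and hospitalization days".

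The other laboratory outcomes with a cut-off each look one way. White cells are an example: "Increase in white blood cell count (>10.000 cells/mm³". C-reactive protein and amylase count only high values, the gas-exchange ratio counts only low ones, and the primary safety outcome on aPTT counts only prolongation.

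The analysis text is generic: "Categorical variables will be evaluated with Fisher's exact test", and "continuous variables will be compared with non-parametric methods such as Mann-Whitney test or U test". Neither sentence is tied to sodium or potassium. No section counts low and high separately, or defines a change from Day 0 for either electrolyte.

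The laboratory row of Table 1 (Days 0, 2, 5, 7 and 8) reads "Complete blood count, D-dimer, aPTT, urea, creatinine, glucose, reactive protein C, blood gas and amylase". It names neither electrolyte. The laboratory form (Figure 3) has no field for either one, including in its arterial gas block.

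**The concern.** A count of patients outside a two-sided range adds two events that a drug effect would move in opposite directions. An upward shift removes low values and adds high ones; a downward shift does the reverse. The pooled total shows only the net result. It can rise, stay level or fall, according to where the control values lie relative to the two limits.

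The protocol says that safety is the trial's main intention. A safety table that can show no difference, or fewer altered values, while one abnormality becomes more common is poorly suited to that. The weakness lies in how the outcome is defined, so more patients would not cure it.

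**Working it through.** **Inputs from the documents.** The limits are 135 and 145 mEq/L for sodium and 3.5 and 5.5 mEq/L for potassium. Allocation is 1:1 with 40 patients followed, so 20 per arm.

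**The plan's own figure.** The documents give no figure for the electrolytes. The 40 comes from the viral-load outcome (30% v 75%, 80% power, two-sided 5%). With the pooled formula and mean proportion 0.525:

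n = [1.96·√(2·0.525·0.475) + 0.842·√(0.3·0.7 + 0.75·0.25)]² / 0.45² = (1.384 + 0.531)² / 0.2025 ≈ 18.1

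That rounds up to 19 per arm, 38 in all, close to the stated 40. It is used here only to supply 20 per arm.

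**Assumptions.** Values are normal, with one reading per patient. Means, SDs and shifts are assumed. Then P(low) = Φ((L − mean)/SD) and P(high) = 1 − Φ((U − mean)/SD), and altered is their sum.

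**Potassium, mean 4.1, SD 0.5, shift +0.4**

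| | Low | High | Altered |
|---|---|---|---|
| Control | Φ(−1.2) = 11.5% | 1 − Φ(2.8) = 0.26% | 11.8% |
| Shifted | Φ(−2.0) = 2.3% | 1 − Φ(2.0) = 2.3% | 4.6% |

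High values rise about ninefold while the pooled count falls. The same pattern holds for all nine combinations of mean 4.0, 4.1 or 4.2 with SD 0.4, 0.5 or 0.6.

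**Sodium, SD 3.5, shift +4, three control means**

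| Control mean | Altered, control | Altered, shifted |
|---|---|---|
| 136 | 39% | 15% |
| 138 | 22% | 22% |
| 140 | 15% | 39% |

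The middle row is a special case: 138 and 142 mirror each other about 140, the midpoint of the range, so the totals must agree. In the last row the pooled count rises with the high values.

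**Counts at 20 per arm (assumed), two-sided Fisher**

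- Control 6 low and 0 high, heparin 0 low and 6 high: pooled 6 v 6, p = 1.00; high values alone 0 v 6, p = 0.020.
- Control 8 low and 0 high, heparin 0 low and 6 high: pooled 8 v 6, p = 0.74, leaning towards heparin; high values alone again p = 0.020.

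**Dilution without cancellation.** For a rise in high values from 5% to 40%, exact Fisher power is 72% on high values alone. Pooled power is 57% with 10% low values in both arms and 47% with 30% in both arms. It is 5% if low values fall from 30% to 5%.

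**What each analysis detects in the potassium example, 20 per arm**

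| Analysis | Rejection rate |
|---|---|
| Fisher, altered (pooled) | 3.3% |
| Fisher, low only | 4.7% |
| Fisher, high only | about 0.007% |
| Mann-Whitney on the values | about 68% (simulation) |

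Expected high values are 20 × 0.26% = 0.05 and 20 × 2.28% = 0.46 patients, so the split count has almost nothing to test.

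The 68% is for the values themselves. The SD of a change from Day 0 is SD·√(2(1 − ρ)), where ρ is the correlation between Day 0 and follow-up. At ρ = 0.5 this is again 0.5 and the power is the same; it is higher for larger ρ and lower for smaller ρ.

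**The case against.** The strongest reply is that the size is wholly assumed. The documents give no electrolyte rates, no spread and no expected direction. What they do say argues against a large systemic effect: the section on inhaled heparin calls systemic absorption minimal, and each nebulization holds 2.5 mg, against doses up to 64 mg in the cited inhalation study. This stands. The point concerns what the definition could hide, and nothing shows that a shift will occur.

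A reader might infer that pooling always masks an upward shift. It does not: in the sodium example with control mean 140, the pooled count rises from 15% to 39%. If abnormalities occur in one direction only, pooling loses nothing.

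A reader might also infer that the plan would report a harm as a benefit. In the potassium example patients outside the range really do become fewer, about 2.4 v 0.9 of 20. Calling that wrong means weighting high values above low ones, which the documents do not do. With a rejection rate of 3.3%, the usual report would be no significant difference.

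Nor does splitting the count make the ninefold rise detectable. With 20 heparin patients there would be no high value at all in 63% of trials.

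Finally, grave individual values can still reach the adverse-event route through CTC-AE grading, committee reporting of severe events and the open fields on the form. Nothing forbids tabulating by direction. That is partial cover: it is not a planned comparison between arms, and it leaves the choice of table until after the data are seen.

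**Conclusion.** The point holds in a limited form. Each electrolyte outcome pools opposite abnormalities, the plan nowhere separates them, and the definitions differ in this respect from the other laboratory outcomes with a cut-off. A one-directional shift could therefore be diluted, cancelled or shown as fewer events. Whether it would be depends on background rates and direction, which the documents do not state. The documents support neither the claim that heparin will shift sodium or potassium nor the claim that the pooled count must mislead.

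The priority is modest. These are two of sixteen listed secondary outcomes, the trial was not sized for them, and the primary safety objective rests on bleeding, aPTT and heparin-induced thrombocytopenia. The change is still worth making, because it is cheap and removes an ambiguity of sign from a safety table.

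**What to change.** 1. Replace each pooled outcome with two: sodium below 135 and sodium above 145, potassium below 3.5 and potassium above 5.5. Count patients separately for each, by arm. A patient with readings beyond both limits during follow-up counts in both rows.
2. State that the change from Day 0 in sodium and in potassium, at one named visit among those in the laboratory row, will be compared between arms with the Mann-Whitney test already named for continuous variables. This comparison carries the power; the split counts are mainly descriptive and make the sign visible.
3. Add sodium and potassium to the laboratory row of Table 1 and to the laboratory form. Without this, neither the present outcomes nor the revised ones have a scheduled, recorded value, and no Day 0 change can be computed.

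The cost is a few lines of wording, two extra count rows and two rows for the continuous comparisons, plus the two added laboratory items. The existing outcomes need those items in any case. No more patients are required.
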